6.2. PRIMARY SAFETY ENDPOINT

Descriptive statistics of safety outcomes will be reported to ensure that device safety performance is clinically meaningful. All adverse events observed during the acute procedure will be tabulated and presented along with the duration, severity, and relatedness to the Jewel EP Lab System. The proportion of subjects experiencing an AE or SAE will also be presented. No formal safety analyses will be performed due to the fact that the sample size does not allow for a powered safety endpoint.

7. STUDY POPULATION

7.1. PATIENT INCLUSION/EXCLUSION CRITERIA

The study will only enroll up to 24 subjects that fulfill the eligibility criteria of the investigation. Subject participation is voluntary and the study will be conducted in accordance with the Declaration of Helsinki.

Inclusion Criteria:

Candidates for this study must meet all the following criteria:

- 1) Subjects of both genders of at least 18 years of age.
- 2) Subjects who are scheduled for a standard EP clinical procedure where life-threatening VT or VF may spontaneously occur or may be induced.

Exclusion Criteria:

Candidates will be ineligible for enrollment if any of the following conditions apply:

- 1) Subjects who may require sterile access to the right upper pectoral or lower left torso regions during the planned EP procedure.
- 2) Subjects who have taken amiodarone in the past 3 months.
- 3) Subjects with an existing unipolar pacemaker.
- 4) Subjects who exhibit a left ventricular ejection fraction (LVEF) less than 20% (as assessed by techniques such as echocardiography, magnetic resonance imaging, or radionuclide angiography within the last 6 months).
- 5) Subjects who have been diagnosed with heart failure (Class IV) or experienced an acute heart failure exacerbation within the previous 30 days.
- 6) Subjects who exhibit unstable angina.
- 7) Subjects with atrial fibrillation with contraindication to anticoagulation or improper anticoagulation management.
- 8) Subjects who are participating in an investigational study of a drug, biologic, or device not currently approved for marketing.
- 9) Subjects who are allergic to or have had a known adverse reaction to medical adhesives.
- 10) Subjects who have active skin breakdown, erythema, or other signs of infection in the pectoral or torso regions where the study device is applied.
- 11) Subjects with a lower abdomen circumference of less than 68.5 cm or greater than 142 cm.
- 12) Females who are pregnant or breastfeeding, or planning to be pregnant in the next 12 months.
- 13) Subjects who cannot provide or have diminished capacity to provide informed consent.
- 14) Any condition that an Investigator believes would interfere with the intent of the study or is not in the best interest of the patient.
- 15) Any patient that according to the Declaration of Helsinki is unsuitable for enrollment.

Note: Subjects with an active implanted device, such as a pacemaker, ICD, or a subcutaneous-ICD, are not excluded in the eligibility criteria, but the Investigator may choose to screen out subjects where the active device or clinical procedure may interfere with the intent of the study.

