6. STUDY DESIGN

This study is a single center, prospective, single arm, non-randomized, non-blinded feasibility study that will be conducted in the European Union. The sample size for the study is a maximum of 24 subjects.

Eligible subjects will be those scheduled for a standard EP procedure where life-threatening VT or VF may spontaneously occur or may be induced. Subjects are excluded if they exhibit a left ventricular ejection fraction (LVEF) less than 20%, have been recently diagnosed with heart failure or have NYHA Class IV heart failure, have unstable angina or atrial fibrillation with a contra-indication to anticoagulation or improper anticoagulation management. The adaptive study design will allow for continuous enrollment of eligible subjects until the sample size is met for the treatment analysis per the statistical plan.

Patients undergoing a standard EP clinical procedure where life-threatening VT or VF may occur are eligible for enrollment in this study. The Jewel EP Lab System will be placed on the subject's torso in the anterior-apical monitoring vector and will be able to deliver an electric shock in the event the patient experiences spontaneous or induced VT or VF.

It is anticipated that the study will require 3 months for enrollment and completion as the study does not require follow-up after the completion of the EP Lab procedure except in the event of adverse events in which case the subject will be followed until resolution. The Sponsor and the Principal Investigator will continuously monitor the safety data (including all reported serious adverse events) throughout the trial.

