6.1. PRIMARY EFFICACY ENDPOINT

The primary endpoint will evaluate the percent of successful terminations of life-threatening VT or VF in subjects who are enrolled in compliance with the protocol-defined entry criteria and are treated with either model of the Jewel EP Lab System. The endpoint will be achieved if the lower confidence limit exceeds the performance goal of 62% using a one-sided exact lower 97.4% confidence bound at one of three testing points. These conditions ensure that performance will be in line with previously published randomized controlled trial results on a relevant comparator, the ZOLL LifeVest, which is the only commercially approved WCD in Europe or the United States. A sequential method of testing will be used to evaluate conversion success. If the Jewel EP Lab System is NOT used to deliver a defibrillation shock during the EP procedure, the subject will not be included in the treatment analysis.

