In cases where the patient is stable, the VT/VF may be allowed to continue for 20-30 seconds to ensure the algorithm has sufficient ECG data to make a rhythm determination over multiple eight-second segments. The timing of the defibrillation shock is under the discretion of the physician to ensure patient safety. In the case where VT/VF is not sustained for the minimum of 8-12 seconds, the indicator light on the Controller Box will not illuminate. The ECG data recorded on the Jewel EP Lab System will also be analyzed post-procedure to assess the performance of the algorithm.

In the event that the defibrillation shock delivered through the Jewel EP Lab System does not successfully terminate the VT/VF, the rescue defibrillator will be used to deliver subsequent defibrillation shock(s).

Throughout the clinical procedure, the Jewel EP Lab System will only be used in appropriate cases based on physician judgment.

- In the case that a defibrillation shock is delivered through the Jewel EP Lab System, the clinical procedure will continue as planned. If a subsequent defibrillation shock is required during the procedure, the rescue defibrillator will be used. The Jewel EP Lab System will only be employed for a single shock during each procedure. In the case that the Jewel EP Lab System is used to deliver a defibrillation shock and the subject meets all enrollment criteria, the subject will be included in the treatment analysis for the primary endpoint.
- In the case that the Jewel EP Lab System is not used to deliver a defibrillation shock during the procedure, the subject will not be included in the treatment analysis to meet the sample size requirements per the statistical plan. In approximately 30 percent of cases, life-threatening VT or VF may not occur or be inducible and therefore an external defibrillation shock would not be required.¹¹ In addition, based on physician judgment, the Jewel EP Lab System may not be used to provide a defibrillation shock during the procedure. In these cases, the subject will not be included in the treatment analysis for the primary endpoint, however, an Intent-to-Treat (ITT) analysis will be performed for informational purpose.

At the conclusion of the acute procedure, the Jewel EP Lab System will be removed from the subject and the Controller Box will be disconnected from the Adhesive Electrode Patches. The subject will exit the study immediately after completion of the EP clinical procedure.

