9. SUBJECT REMOVAL FROM STUDY

Only subjects that meet all enrollment criteria and have received a defibrillation shock will be included in the treatment analysis, however all subjects enrolled, whether or not receiving a defibrillation shock, will be included in the reporting of study results.

Overall, if a subject drops out of the study at any time due to an adverse event or for any other cause, the reason for discontinuation, the nature of the event, and its clinical course must be fully followed and documented. In the case of an adverse event, the Investigator must strive to follow the subject until the adverse event has either resolved, become clinically insignificant, the event is stabilized, or the subject is lost to follow-up.

If at any point during the study, the patient withdraws consent or the Investigator assesses that the risks to the subject outweigh the benefits of participation in the study, the subject will be discontinued. If, during the course of the study, the Investigator feels that, in his/her best clinical judgment, the study should be prematurely terminated, he/she will notify the Sponsor and give the reason(s) for this decision. If the Sponsor decides, based on data or internal information, that it would be prudent to discontinue temporarily or to terminate the study, the Sponsor will inform the Investigator of this decision and the reason(s) for the decision.

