For the calculation of sample size, this study will use an anticipated first shock conversion success rate of 87.5% in the EP Lab Study with a performance goal of 62%, the same as the first shock success rate seen in VEST. The performance of the Jewel will be considered acceptable if the lower confidence limit exceeds the performance goal of 62% (green line in the graph on page 24).

The sample size for this study is a maximum of 24 subjects. Subjects can be treated with either the ES-1 or the ES-2 model of the Jewel EP Lab System, as the devices are representative of each other. This sample size is based on a group sequential design measuring the observed proportion of successful life-threatening VT or VF terminations. The group sequential design uses a Pocock alpha spending function and allows for testing after 12, 18, and 24 subjects are enrolled. The design controls the overall Type I error rate at 5%. In line with the Pocock alpha spending function, a one-sided lower 97.4% exact confidence bound will be calculated using the exact binomial (Clopper-Pearson) method at each testing point.

Primary Endpoint Analysis:

Upon completion of the Jewel EP Lab Study, all clinical data from both the ES-1 and ES-2 models of the Jewel EP Lab System will be pooled, as the devices are representative of each other. The primary endpoint will evaluate the percent of successful terminations of life-threatening VT or VF in subjects who are in subjects who are enrolled in compliance with the protocol-defined entry criteria and treated with the Jewel EP Lab System (either ES-1 or ES-2 model).

Using the VEST RCT results for the first shock success as a guide, the performance goal of 62% was established for the Jewel EP Lab Study. The endpoint will be achieved if the lower confidence limit exceeds the performance goal of 62% using a one-sided lower 94.5% exact confidence bound at one of the three testing points.

These conditions ensure that performance will be in line with previously published randomized controlled trial results on a relevant comparator, the ZOLL LifeVest which, is the only commercially approved WCD in Europe or the US. The method for testing the conversion success will follow these steps:

1. If after attempting to convert the first 12 subjects, all subjects have been successfully converted (100% conversion rate) the trial will be stopped and deemed a success. Otherwise, continue to Step 2.

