2. If conversion is less than 100% after 12 total subjects, enroll six (6) additional subjects for a total of 18 subjects. If 17 out of the 18 are successfully converted (94.4% conversion rate), or if 16 out of the 18 are successfully converted (88.0% conversion rate), the trial will be stopped and deemed a success. Otherwise, continue to Step 3.
3. Enroll the final six (6) subjects for a total of 24 subjects. If after attempting to convert 24 subjects, 21 of the 24 are successful (87.5% conversion rate), the trial will be deemed a success.

A 100% conversion rate with 12 subjects results in a one-sided lower 97.4% exact confidence bound of approximately 73.7% which exceeds the 62% performance goal.

[figure not shown]
With a sample size of 18 subjects with 1 failure, the conversion rate is 94.4% with a one-sided lower 97.4% exact confidence bound of approximately 72.8% which also exceeds the 62% performance goal.

With a sample size of 18 subjects with 2 failures, the conversion rate is 88.9% with a one-sided lower 97.4% exact confidence bound of approximately 65.4% which also exceeds the 62% performance goal.

With a sample size of 24 subjects with 3 failures, the conversion rate is 87.5% with a one-sided lower 97.4% exact confidence bound of approximately 67.8% which also exceeds the 62% performance goal.

All of these scenarios result in a successful trial as the one-sided lower 97.4% exact confidence bound is above the performance goal of 62%. If at any point during the course of this study there are more than three (3) failures to convert a shockable rhythm (life-threatening VT or VF) due to the Jewel, the study will be stopped and deemed unsuccessful.

The graph below summarizes the group sequential study design, conversion success, and results of the one-sided lower 97.4% exact confidence bound.

Overall Type I Error Discussion:

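### The limit of 24 and the looks at 12, 18 and 24 are tied to enrolled subjects in some sections and to treated subjects in others; with about 30% unshocked, the rules cannot all be followed

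*Combined protocol and SAP*

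**What the plan says.** Two units are in use for the same numbers.

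**Enrolled.** Section 7.1: "The study will only enroll up to 24 subjects that fulfill the eligibility criteria of the investigation". Section 11.1 says the group sequential design "allows for testing after 12, 18, and 24 subjects are enrolled". Steps 2 and 3 in Section 11.1 also speak of enrolling six further subjects each.

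**Treated.** Step 3 reads "If after attempting to convert 24 subjects, 21 of the 24 are successful", and Step 1 likewise counts attempted conversions. Section 9: "Only subjects that meet all enrollment criteria and have received a defibrillation shock will be included in the treatment analysis". Section 8.2 says of a subject who gets no shock from the device that "the subject will not be included in the treatment analysis to meet the sample size requirements per the statistical plan". Section 6 (and the Synopsis in near-identical words) provides for "continuous enrollment of eligible subjects until the sample size is met for the treatment analysis per the statistical plan".

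**Expected non-use.** Section 8.2: "In approximately 30 percent of cases, life-threatening VT or VF may not occur or be inducible". It adds that physician judgment may lead to further non-use.

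**Success criterion.** Section 6.1 calls the endpoint met if the lower limit "exceeds the performance goal of 62% using a one-sided exact lower 97.4% confidence bound at one of three testing points". The Synopsis, Section 6 and Section 11.1 each give a maximum of 24 subjects without saying enrolled or treated. No section gives an enrolment limit above 24.

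**The concern.** If about three in ten enrolled subjects never enter the analysis, 24 enrolled and 24 treated cannot both be the size of this trial. A site that observes Section 7.1 will almost never reach the 24-subject step. A site that observes Section 6 will often enrol more than the stated limit.

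The choice can also change the verdict. Suppose 24 are enrolled, 17 treated and 15 converted. Read with the enrolment-timed third look of Section 11.1, the bound criterion in Section 6.1 is met. The numbered steps give no conclusion, because 17 is past the 12-subject step and short of the 18-subject one. The study is not blinded, so a decision on the wording taken at that stage would be made with the tally known.

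**Working it through.** **Inputs.** Performance goal 62%, anticipated conversion 87.5%, one-sided 97.4% Clopper-Pearson bound, and success rules 12/12, at least 16/18 and 21/24 (Section 11.1). Stop as unsuccessful at more than three failures (Section 11.1); I count every failure as attributable to the device. Shocked fraction 70%, from the 30% in Section 8.2, taken as independent between subjects and independent of conversion.

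**1. The plan's own bounds.** The lower bound for x of n is the 0.026 quantile of Beta(x, n − x + 1).

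| Result | Stated | Recomputed |
|---|---|---|
| 12/12 | 73.7% | 73.8% |
| 17/18 | 72.8% | 72.9% |
| 16/18 | 65.4% | 65.5% |
| 21/24 | 67.8% | 67.8% |

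They agree to 0.1 point, so the decision rules work on treated denominators.

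**2. Success with 24 treated, at 87.5%.**

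- Look at 12: 0.875^12 = 0.2014.
- Look at 18: P(at most 2 failures in 18) − P(none in the first 12 and at most 2 in the next 6) = 0.6051 − 0.2014 × 0.9709 = 0.4095.
- Look at 24: exactly 3 failures by 18, at least one of them in the first 12, then none in the last 6 = (0.2150 − 0.0053) × 0.4488 = 0.0941.
- Total: 0.705. Every other path ends at a fourth failure, so on treated counts the steps always reach a conclusion.

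Section 11.1 states 90% power. That this is not reproduced is a separate matter.

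**3. Treated subjects if enrolment stops at 24.** T ~ Binomial(24, 0.70), mean 24 × 0.70 = 16.8. P(T ≥ 12) = 0.9885, P(T ≥ 18) = 0.3886, P(T = 24) = 0.00019.

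**4. Outcomes under that cap.**

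- Success: 0.2014 × 0.9885 + 0.4095 × 0.3886 + 0.0941 × 0.00019 = 0.358.
- Stopped for failures (exact recursion over treated count and failures): 0.152.
- Neither: 1 − 0.358 − 0.152 = 0.490. This divides into 0.407 with 12–17 treated, 0.072 with 18–23 and 0.011 with fewer than 12.
- Neither, although the 97.4% bound on those treated exceeds 62%: 0.192 of all trials.

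**5. Sensitivity to the shocked fraction, cap of 24 enrolled.**

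| Shocked | 18 treated reached | Success | Undecided |
|---|---|---|---|
| 60% | 10% | 22% | 68% |
| 70% | 39% | 36% | 49% |
| 75% | 61% | 45% | 37% |
| 80% | 81% | 53% | 26% |
| 90% | 99% | 62% | 13% |

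**6. Verdict example.** The 97.4% bound for 15/17 is 63.8%, above 62%; for 14/16 it is 61.9%, just below.

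**7. Looks timed by enrolment.** If the 97.4% bound is applied to those treated so far when 12, 18 and 24 are enrolled, success is 58.3% at 70% shocked.

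**8. Type I error at a true rate of 62%.** 1.6% with 24 treated, 0.7% with 24 enrolled and the step counts, 2.3% with enrolment-timed looks. All are below 5%.

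**9. Enrolment needed for 24 treated.** On average 24/(1 − 0.30) = 34.3, so 35.

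| Enrolment ceiling | P(24 treated available) | Success | Mean enrolled |
|---|---|---|---|
| 35 | 65% | 67.0% | 24.1 |
| 39 | 91% | 69.6% | 24.3 |
| 41 | 96% | 70.1% | 24.3 |

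Mean enrolment under the cap of 24 is 21.5. With a higher ceiling, 49% of trials pass 24 enrolled; these are the trials left undecided in step 4.

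**The case against.** The strongest reply is that the intent is plain. The Synopsis, Section 6 and Section 8.2 tie the sample size to the treatment analysis, Sections 6.1 and 9 confine that analysis to shocked subjects, and every printed bound has a treated denominator. On that reading enrolment simply continues, no power is lost, and the 35.8% and 49.0% never arise. This largely stands as a guide to intent, and the capped figures should be read as conditional on the less-supported reading. It does not remove the conflict: Section 7.1 is an explicit limit, Section 12.4 commits the investigator to strict adherence, and the favoured reading breaks that limit without putting another in its place.

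Second, a trial that meets no success rule could be taken as not having met the endpoint, so undecided may be too strong a word. That is a reasonable inference, but Section 11.1 declares the study unsuccessful only after more than three failures, and says nothing about running out of enrolment.

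Third, the 15/17 example combines the enrolment-timed look with the general bound criterion and sets aside the numbered steps. True; it shows what the wording permits, not how the trial would most likely be run.

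Fourth, some side figures depend on other choices. Section 11.1 also gives a 94.5% bound for the same endpoint; with it, the 19.2% becomes 35.7%. The failure stop is limited to failures attributable to the device, so the division between stopped and undecided could shift. Neither affects the contradiction.

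**Conclusion.** The concern holds and needs correction before the trial relies on these rules. The enrolment limit, the timing of the looks and the denominators of the success rules use different units, and at the protocol's own 30% non-use they cannot all be met. Taken literally, the cap halves the chance of success (70.5% to 35.8%) and leaves 49.0% of trials with no conclusion under the steps. Taken as treated subjects, the design works as its bounds require, but about half of trials exceed the enrolment limit in Section 7.1. There is no inflation of Type I error on any reading computed.

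The sizes rest on 70% shocked, independence between subjects, 87.5% conversion, the 97.4% bound, and all failures counting towards the stop. The contradiction rests on none of these beyond some subjects going unshocked, which Section 8.2 expects.

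**What to change.** State once that the maximum of 24 and the looks at 12, 18 and 24 count treated subjects, using the protocol's existing definition (eligible, and shock delivered by the study device). Bring into line the enrolment cap in Section 7.1, the look timing in Section 11.1 and the references to enrolling in Steps 2 and 3. Give a separate enrolment ceiling together with its assurance at 30% unshocked, for example from the table of ceilings of 35, 39 and 41. If 24 enrolled is what is meant, restate instead the looks, the decision rule at each possible treated count, and the power.

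The cost is an amendment and a revised number for the ethics committee and the consent form, since Section 8.1 requires subjects to be told the approximate number involved. A ceiling of 35 to 41 means up to 11 to 17 more people consented and fitted with the device, within a study planned for 3 months. Because of early stopping, mean enrolment rises only from 21.5 to about 24.3, and no more subjects are treated than the decision rules already require.

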8. STUDY ACTIVITIES

The Study Activities are detailed in Table 8.1.

Table 8.1: Study Activities

Study Activity	Pre-Procedure	Intra-Procedure	Post-Procedure
Informed Consent	X		
Screening Visit	X		
Medical History/Clinical Status	X		
Skin Preparation & Device Placement (including photograph)		X	
Therapy Delivery		X (if applicable)	
Device Removal		X	
Adverse Events Assessment		X	X (if applicable)

8.1. SUBJECT ENROLLMENT

All patients admitted for an EP lab procedure will be screened for study eligibility. A member of the research team will review the patient's medical history for eligibility. A screening log will be maintained by each site and completed for all patients screened. The screening log will identify the reason(s) potential study subjects were not enrolled into the trial. If all inclusion criteria are met and no exclusion criteria are present, the patient will be presented with the Ethics Committee-approved Patient Informed Consent (PIC). This consent form will comply with all applicable local, state and federal regulations governing the protection of human patients. The Investigator must provide the Sponsor with a written copy of the PIC that the IEC reviewed, and the IEC approval of the PIC prior to enrollment of any subjects.

It is the responsibility of the Investigator to obtain written informed consent from each subject or the legally authorized representative of the subject prior to the initiation of any study-related procedures. Each prospective study subject must be informed of:

- The purpose, procedures, and expected duration of the subject's participation;
- Potential hazards/risks to the subject;
- Anticipated benefits to the subject or others;
- Disclosure of appropriate alternate procedures/treatments;
- A statement describing the extent, if any, to which confidentiality of records identifying the subject will be maintained and notes that the FDA and the Sponsor may inspect the records;
- An explanation of any compensation and an explanation as to whether any medical treatments are available if injury occurs and, if so, what they consist of, or where further information may be obtained;
- An explanation of whom to contact for answers to questions about the research and research subjects' rights, and whom to contact in the event of a research-related injury to the subject;
- A statement that participation is voluntary, that refusal to participate or withdrawal at any time will involve no penalty or loss of benefits;
- A statement that the particular treatment or procedure may involve risks to the subject (or to the embryo or fetus, if the subject is or may become pregnant) which are currently unforeseeable;
- Anticipated circumstances under which the subject's participation may be terminated by the Investigator without regard to the subject's consent;
- Any additional costs to the subject that may result from participation in the study;
- The consequences of a subject's decision to withdraw from the research and procedures for orderly termination of participation by the subject; and
- The approximate number of subjects involved in the study.

Each subject will be given a signed copy of the Patient Informed Consent.

Signed PIC Forms must be retained in the study file by the Investigator, and be available for review by the Sponsor and/or regulatory agencies, as applicable. The time and date consent was rendered will be documented in the subject's medical record.

The PIC and any other written information provided to subjects will be revised whenever important new information becomes available, or if there is an amendment to the protocol which necessitates a change to the content of subject information and/or to the consent form. The Investigator will inform the subject of changes in a timely manner, and will ask the subject/patient to confirm his/her continuation in the study by signing a revised consent form. Any revised PIC Form and other written information provided to subjects must receive IEC, Sponsor, and regulatory agency approval, as applicable.

At the Screening visit the subject's baseline information will be collected, including demographics, medical history and cardiac-related test results, and will undergo a basic physical exam.

